Recently, imaging modalities have garnered much interest in identifying structural and functional changes in the brains of patients with central sensitivity states. In fibromyalgia patients, there is both decreased and increased grey matter volume and increased connectivity in brain areas responsible for the anticipation of, attention to, and emotional processing of pain (21-23). Resting state functional magnetic resonance imaging (fMRI) scans measure basal metabolic signatures during periods of "rest" that can reveal underlying connectivity of different areas of the brain and have been shown to be amplified in patients with central sensitization syndromes such as fibromyalgia, chronic fatigue, irritable bowel syndrome, temporomandibular joint disorder patients (24). Structural alterations such as grey matter volume can also be measured using structural MRI measurements in areas of the brain that are associated with stress, pain, emotional processing, and memory development. A combination approach of quantitative sensory testing (25) along with fMRI imaging has been used to correlate pain thresholds with brain activity in the fibromyalgia patients (23). In these studies, a stimulus of increasing intensity (vibratory, thermal, or pressure) is administered in a step-wise fashion and changes in blood flow (and therefore activity) to specific brain regions are assessed. These types of studies have shown that lower pain thresholds correlate well with earlier activation of pain centers in patients with fibromyalgia when compared to negative controls. Although these studies have made great strides in unveiling the dynamic processes involved in central sensitization, the sequential events leading to the development of the central sensitivity syndromes are still unknown. This is because the existing literature only provides a snapshot of ongoing pathological pain processes since these patients present only after

disease onset. This is supported by the conflicting structural and functional MRI data in the literature which is likely due to a heterogeneous patient population who may be in distinct stages of disease progression.

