The answers to these questions will provide us with the foundation for future studies in which we hope to characterize the evolution and progression of central sensitization in this unique patient population. This will allow us to eventually guide personalized treatment regimens for treating and preventing central pain in the cancer population using multimodal, non-opioid based regimens. It will also provide us with a rare opportunity to expand our knowledge in the pathogenesis of central sensitization that will be globally applicable to other centralized pain syndromes.

2.0 Study Summary and Specific Aims:

Summary: We propose to conduct a cross-sectional pilot study of H&N cancer survivors who have completed multimodal treatment to assess and characterize the presence of distinct pain syndromes. We plan to screen patients who have completed head and neck cancer therapy using a battery of patient reported outcome measures (PRO's). Based on the PRO responses, patients will be characterized as follows: 1) no pain, 2) central pain, and 3) nociceptive pain. Patients will then undergo structural and functional magnetic resonance imaging

(MRI). We will correlate clinical presentation with MRI signatures to determine if distinct signatures can be identified for each cohort. In addition, we propose to correlate the clinical and MRI signatures for central pain with the presence of other systemic symptoms. Participants will be asked to fill out several questionnaires that capture systemic symptoms commonly associated with other central sensitivity syndromes.

Aim 1: To correlate structural and functional MRI signature with one of three pain phenotypes in H&N cancer survivors: 1) no pain, 2) central pain, and 3) nociceptive pain.

Hypothesis 1: Structural and functional MRI can identify unique signatures that correspond with pain phenotype.

Aim 2: To correlate the presence of chronic systemic symptoms with pain phenotype.

Hypothesis 2: Patients with central pain will have an increased frequency of other systemic symptoms (fatigue, neurocognitive dysfunction, depression, etc.) as measures on the General Symptom Survey.

Exploratory Aim: DNA, RNA, and plasma will be collected for genomic, transcriptomic, and proteomic studies. Results will be vertically integrated along with the results of clinical studies described within this protocol to identify targets for future correlative studies.

3.0 Methods:

Patient Eligibility:

Inclusion Criteria:

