- Patients with histologically proven head and neck cancer
- Patients without a diagnosis of head and neck cancer (up to 10 patients, see below)
- Completed multi-modality therapy a minimum of 6 weeks prior to study entry.
- Willing and able to provide informed consent
- All participants must be at least 21 years of age
- Able to speak English

We anticipate enrolling a total of 75 patients with a history of head and neck cancer who will complete all questionnaires and MRI scanning. We will also recruit up to 10 patients WITHOUT a diagnosis of head and neck cancer to facilitate optimization of the MRI scanning processes. This will allow us to address logistical issues, such as pressure stimulator setup and timing of each scan to be performed.

Exclusion Criteria:

- Patients who are pregnant. See below under “Study Procedures” section on pregnancy testing.
- Patients who are unable to lie still.
- Patients who are unable tolerate pressure stimulator.
- Non-MRI compatible devices such as aneurysm clips, cardiac pacemakers or defibrillators, cochlear implants, hardware, or any other implants
- Iron-based tattoos, pieces of metal (bullet, BB, shrapnel) close to or in an important organ (such as the eye), or other non-MRI compatible metal in the body.

Study Procedures:

Recruitment

The attending physicians, nurse practitioner or nurses in the Oncology Clinic routinely review the list of patients presenting to clinic for follow-up visits. All patients who are a minimum of 6 weeks post treatment will be provided with information about the study and asked if they are interested in study participation. If patients express interest, trained study staff will be notified. Study staff will meet with all interested patients to discuss the study in more detail and answer questions.

Informed Consent Process

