The average time to test completion is less than 12 min based on the literature. We believe that most patients will be able to tolerate this stimulus. In a recent study by Harte *et. al.* (28), tolerability of the pressure stimulus was high and only 10 out of 298 patients opted out. They were able to obtain data for 62 patients with urologic chronic pelvic pain syndrome at the initial visit and 52 measurements at a 6 month follow-up visit. In fact, the pressure pain stimulus protocol has been adapted from this article. However, those who are unable to tolerate the stimulus will not be included in the anticipated accrual goal count.

Since the initiation of study, we have recruited and tested 3 subjects. For those who have already completed the study, we will attempt to repeat the pain threshold and tolerance testing along with the slowly repeated evoked pain testing during a future clinic appointment. All other enrolled subjects who have not completed the study will undergo the entirety of the protocol on the day of MRI scanning.

Exclusion of Pregnant Women

Although MRI has not shown to affect pregnancy, those who are pregnant will be excluded from the study. Women of reproductive age will be asked to take a pregnancy test after informed consent has been obtained. The pregnancy test will be conducted on the day of the MRI scan. Those who have had bilateral oophorectomies, hysterectomy, and/or tubal ligations will be excluded from pregnancy testing. If pregnancy test is declined, the patient will be excluded from the study.

PRO Data Collection

Disease and treatment data (e.g. type and stage of cancer, date of cancer diagnosis) will be obtained from the participant's medical record review by study staff at Vanderbilt.

After patients have signed informed consent, they will be scheduled for study related activities at a time that is convenient to them. All patients will complete the Sociodemographic Data Collection Form, the Vanderbilt Head and Neck Symptom Survey plus General Symptom Survey Version 2.0, Profile of Mood States-Short Form, Neurotoxicity Rating Scale, the Quality of Life Assessment, Central Sensitivity Inventory, the Fibromyalgia Diagnostic Tool, and the Head and Neck Pain Inventory.

Blood Draw:

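### The eligibility rules contain no exclusion or screen for known brain disease, although Aim 1 compares brain MRI across three cohorts of 25

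*Combined protocol and SAP*

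**What the plan says.** Section 3.0, Patient Eligibility, has five exclusions:

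- pregnancy ("Patients who are pregnant. See below under" the study-procedures text);
- stillness: "Patients who are unable to lie still";
- the stimulus: "Patients who are unable tolerate pressure stimulator";
- devices: "Non-MRI compatible devices such as aneurysm clips, cardiac pacemakers or defibrillators, cochlear implants, hardware, or any other implants";
- certain tattoos, metal fragments "or other non-MRI compatible metal in the body".

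The inclusion criteria concern cancer history, completed treatment, consent, age and language. The Recruitment text filters only on time since treatment.

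Aim 1 in section 2.0 is "To correlate structural and functional MRI signature with one of three pain phenotypes in H&N cancer survivors". Under Phenotype Designation, 25 patients per cohort go to MRI. Section 4.0 lists structural, resting-state, stimulus-evoked and diffusion imaging.

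Under PRO Data Collection, disease and treatment data "will be obtained from the participant's medical record review by study staff". The examples given there are cancer type, stage and date of diagnosis.

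**The concern.** All five exclusions serve scanner safety or feasibility. None protects the meaning of a brain measurement. A stroke, metastasis or resection can alter grey-matter volume, diffusion measures and functional signal for reasons unrelated to pain phenotype. With 25 scans per cohort, a single atypical brain carries weight in the cohort mean and more weight in its variance.

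Two effects follow. If affected patients are spread evenly, the comparison becomes noisier. If they gather in one cohort, it becomes biased. Gathering in the central-pain cohort is plausible. The Central Sensitivity Inventory and the Fibromyalgia Diagnostic Tool help assign cohorts, and both score systemic symptoms. The background treats fatigue, cognitive dysfunction and mood disturbance as part of the central picture, and brain disease can produce the same complaints.

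**Working it through.** **Step 1: does any other section close the gap?**

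| Place | What it does | Handles known brain disease? |
|---|---|---|
| 3.0 Inclusion Criteria, Recruitment | Cancer history, treatment completed, at least 6 weeks elapsed, consent, age, language | No |
| 3.0 Exclusion Criteria | Five items above; aneurysm clips appear as a scanner hazard | Only incidentally |
| 3.0 PRO Data Collection | Record review of disease and treatment data | Neurological history not named |
| 3.0 Phenotype Designation | Cohorts assigned from three questionnaires | No |
| 4.0 Central Sensitivity Inventory, Part B | Prior diagnoses of central sensitivity and related disorders; not scored | Not an exclusion |
| 4.0 MRI protocol | Acquisition and physiologic recording | No rule for scans with lesions |
| 10.0 Statistics and Sample Size | Analysis of variance for Aim 2 symptom subscales | No MRI analysis, no covariate |

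The gap is not closed elsewhere.

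**Step 2: inputs for a size.** The only power figure in the plan (about 25 per group for a difference of 0.35 at 80% power) belongs to the Aim 2 subscales. It is given without SD or alpha, so it cannot be reproduced and does not bear on MRI. For Aim 1 the documents give only n = 25 per cohort. The following are my assumptions: two-sample t-test at two-sided 0.05, true difference 0.8 SD between the central and a reference cohort, and a brain lesion that adds s = 1, 2 or 3 SD to the affected patient's value, in the direction of the central cohort's mean.

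**Step 3: what one patient does to a cohort of 25.**

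- Mean shift = s/25, that is 0.04, 0.08 or 0.12 SD.
- Expected sample variance = 1 + s²/25, that is 1.04, 1.16 or 1.36.

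For s = 3 in the reference cohort, the standardized difference falls from 0.8 to (0.8 − 0.12)/√((1 + 1.36)/2) = 0.68/1.086 = 0.63. For one such patient in each cohort it is 0.8/√1.36 = 0.69.

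**Step 4: simulated rejection rates** (200,000 replicates per cell; smaller runs differ by about one point).

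| Affected patients | s = 1 | s = 2 | s = 3 |
|---|---|---|---|
| None, true difference 0.8 SD | 79% | 79% | 79% |
| One, reference cohort | 74% | 68% | 59% |
| One in each cohort | 78% | 74% | 68% |
| One, central cohort | 82% | 84% | 85% |
| No true difference, one in central cohort | 5.0% | 5.0% | 4.9% |
| No true difference, two in central cohort | 5.5% | 6.5% | 7.6% |

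The rise in the fourth row is not a gain: the lesion inflates the apparent cohort difference.

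**Step 5: how likely is one affected patient?** The documents give no prevalence. If 2%, 5% or 10% of eligible survivors were affected, the expected number among 75 scans is 1.5, 3.75 or 7.5. The chance of at least one in a given cohort of 25 is 1 − (1 − p)²⁵ = 40%, 72% or 93%. These prevalences are assumptions that show the range only.

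**The case against.** The best defence is that this is a single-centre, cross-sectional pilot, and that broad eligibility is a legitimate choice. Consent capacity, the lie-still rule and the device rule will remove some affected patients. That is true, but they do not remove a survivor with an old stroke who can consent and lie still.

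The size is also open to challenge, and this part stands. Section 10.0 plans no t-test and no imaging effect of 0.8 SD. The largest power losses require both a large shift and the unfavourable direction. A gentler model, which treats affected scans as having 2 to 3 times the usual SD, takes power (80.7% by normal approximation) only to 78–75% at 2% prevalence and 75–67% at 5%.

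Four stronger readings are tempting and are not supported:

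- A reader might take the background's remark on "conflicting structural and functional MRI data in the literature which is likely due to a heterogeneous patient population" as the protocol's own admission. That sentence goes on to refer to stages of disease progression, not to brain comorbidity.
- A reader might suppose that image quality control is planned but would miss lesions. The documents describe no image quality control at all.
- A reader might call MRI the designated primary outcome. No primary outcome is designated; its weight comes from being Aim 1 and from cohorts being filled for scanning.
- A reader might conclude that cohort differences will be spurious. Clustering is plausible, but nothing in the documents shows that it occurs.

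**Conclusion.** The omission is certain on the text: applied exactly as written, the plan admits patients with known brain disease to the Aim 1 comparison and provides no adjustment for them. The consequence is uncertain in size. Under the stated assumptions, one affected patient costs between about 1 point of power (one in each cohort, 1 SD) and about 20 points (reference cohort only, 3 SD). One affected patient produces no visible false-positive inflation; two in the central cohort raise the rate to at most about 8%. The result does not show that Aim 1 would fail. It shows an avoidable source of noise, with possible bias, in a small comparison meant to guide later studies. The change is worth making because it is cheap.

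**What to change.** Add to the Exclusion Criteria in section 3.0: documented stroke, intracranial tumour or metastasis, brain surgery, or other structural or neurodegenerative brain disease. Establish this from the medical-record review already described under PRO Data Collection, and name neurological history there as a data item.

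Optionally, record from the treatment record whether brain tissue lay in the radiation field, and repeat the Aim 1 comparison without those patients as a sensitivity analysis.

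The cost is a few otherwise eligible survivors, one or two added record items and, if adopted, one extra analysis. Because recruitment continues until all three cohorts are filled, the number scanned need not fall. A rule based on reading every scan for lesions blind to cohort is not proposed: section 4.0 plans no such read, and it would need an additional reader.

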Head and neck (H&N) cancer patients often undergo rigorous treatments which involve chemotherapy, radiation, and surgery. As a result, these patients are highly susceptible to the development of acute and chronic pain. Initially, pain in this population can manifest as acute, well-localized nociceptive pain or neuropathic pain from direct nerve injury. In most cases, these types of pain can be treated with NSAIDs, acetaminophen, and/or opioids during treatment. However, some patients will gradually develop an increasing sensitivity to pain that extends beyond the course of treatment. In extreme cases, patients experience exaggerated pain responses to noxious stimuli (hyperalgesia), painful responses to innocuous stimuli (allodynia), pain in areas unaffected by cancer or its related treatments, and other systemic symptoms of neurological impairment such as fatigue, cognitive dysfunction, and mood disturbances. In this particular subset of patients, the pathogenesis of this exaggerated pain phenotype is highly reminiscent of an amplified pain state also known as central sensitization. In the presence of a repetitive noxious stimulus, the threshold for pain in nociceptive receptors is lowered as a protective mechanism (primary hyperalgesia) (6). The exaggerated response to pain eventually returns to baseline after removal of the stimulus. However, in chronic pain states, overamplification of the nociceptive pathway and dysfunction of inhibitory pathways in the central nervous system leads to permanent pathological pain amplification, known as central sensitization. This manifests clinically as secondary hyperalgesia (pain outside of the site of injury), allodynia, and/or widespread pain (7).

The literature regarding pain in cancer survivors is still in its infancy given the increasing number of curative therapies leading to longer rates of survival after treatment. What we are just now starting to realize is that specific pain phenotypes are unique to specific types of cancers and consequently require different types of pain regimens. However, lack of education and consensus definitions in the classification of pain have resulted in continued opioid use long after commencement of cancer treatment, leading to increased tolerance and escalating doses in the cancer survivor population. Perhaps the most well documented cancer pain syndrome is post-mastectomy pain syndrome (PMPS). The incidence of pain after breast surgery has been reported to

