About 20% of the H&N cancer population develop long-term pain and systemic symptoms after treatment. However, the risk factors associated with the presumable development of central sensitization in this specific patient population have not been identified. To better understand the molecular basis of this treatment complications, patients will undergo phlebotomy for future molecular analyses. DNA, RNA, and plasma will be collected for genomic, transcriptomic, and proteomic studies. Results will be vertically integrated along with the results of clinical studies described within this protocol to identify targets for future correlative studies.

At the time of MRI, blood will be drawn from each patient. Up to 20 ml of blood will be divided for RNA, DNA, and plasma extraction. A portion of the blood will be divided into PAXgene tubes for RNA extraction. The remainder of the blood will be separated into plasma for proteomic analysis and cells for DNA extraction. Samples will be stored at -80C until ready for processing.

Phenotype Designation:

Following completion of the questionnaires, the patient's responses will be reviewed by the principle investigator. Patients will complete the Central Sensitivity Inventory questionnaire, the Fibromyalgia Diagnostic Tool, and the Head and Neck Pain Inventory to determine inclusion into each cohort. Using criteria established in the non-oncologic patient population, patients will be assigned to one of three cohorts by three independent reviewers ([name], [name], and [name]): those with 1) no pain, 2) central pain and 3) nociceptive pain. At least two out of three reviewers must agree with each assignment. 25 patients from each of the principle cohorts will proceed to structural and functional MRI testing. Recruitment will continue until all three cohorts are filled. The patient's participation will be concluded.

Structural and Functional MRI Testing:

The study staff will schedule MRI testing at a time that is convenient for the patient. The procedure will take approximately 1.5-2 hours.

Compensation:

Upon completion of the MRI, patients will be provided with a \$50.00 gift card to compensate them for their time and effort.

4.0 Measures:

Questionnaires:

Demographic Data Form: Patients will be asked to report their birthdate, gender, race, ethnic category, highest educational level, marital status, employment status, area of residence, insurance coverage, and annual household income.

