Vanderbilt Head and Neck Symptom Survey plus General Symptom Survey version 2.0 (VHNSS v2.0 plus GSS): The VHNSS v2.0 (31) assesses the prevalence and severity of treatment-related symptoms and their functional impact in patients with head and neck cancer. The VHNSS v.2.0 consists of 50-items within 13 domains including nutrition, swallowing, xerostomia, mucositis, excess mucus, speech, hearing, taste change, smell, dental health, mucosal sensitivity, range of motion, and pain. Items are scored on a numeric scale rating the severity of the symptom from 0 (none) to 10 (severe). The VHNSS v.2.0 takes approximately 10 minutes to complete. VHNSS v2.0 plus GSS includes 12 additional items directed at the systemic effects of therapy.

Profile of Mood States-Short Form (POMS-SF): The POMS-SF is a 37-item scale is composed of six subscales: depression, vigor, confusion, tension, anger and fatigue. Cronbach's alphas ranged from 0.78 to 0.91. It correlates well with other measures of mood and physical function, yet it has the benefit of a short administration time.

Neurotoxicity Rating Scale (NRS): The NRS is a 37 item instrument whose items reflect symptoms associated with neurotoxicity of medical treatment (32). Participants rate the severity of all of the 37 item, 5 point Likert-like scale that rates neuropsychiatric symptoms on a scale of "not present" to "extremely severe."

Quality of Life: QOL will be measured using Cantril's Ladder, a single item self-anchoring scale (33, 34). The measure asks patients to rate their current quality of life on a scale ranging from 0 to 10, with higher scores indicating better overall quality of life. Discriminant validity has been supported by significantly lower scores in patients with rheumatoid arthritis than in healthy controls (35). Construct validity has been supported by a positive relationship between scores on to social role retention in survivors of bone marrow transplantation (36). A 5 item domain-specific QOL questionnaire will also be used.

Central Sensitivity Inventory (CSI): The CSI is a two-part survey consisting of 35 questions (37). Part A asks patients to identify systemic symptoms as being present "never", "rarely", "sometimes", "often", or "always". Part B determines whether patients have been previously diagnosed with central sensitivity syndromes or other related disorders. Only Part A is used for scoring.

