Fibromyalgia Diagnostic Tool (FDT): The FDT is a questionnaire developed based on the revised American College of Rheumatology's diagnostic criteria for fibromyalgia from 2016 (38). It combines the widespread pain index and the symptom severity scale to aid in the diagnosis of fibromyalgia and the severity of the disease. We will adapt the use of this diagnostic tool for the H&N cancer patient population to detect the presence of a central sensitivity phenotype.

Head and Neck Pain Inventory (HNPI): The HNPI is a diagram in which patients can document specific areas of pain with an emphasis on the head and neck region. The patients are also asked to rate their pain on a scale

of 1-10 in the past week, describe the type of pain they are experiencing, and document any treatments for their pain.

Opioid Risk Took (ORT): The ORT is a self-reporting screening tool for adults to assess the risk for potential opioid abuse in patients with chronic pain. A score of <3 indicates low risk, 4-7 moderate risk, and >8 high risk (39).

MRI protocol:

Standardized protocols developed by investigators in the Imaging Center will be used for the structural and fMRI sessions. The scans will be acquired in order of importance. The study PI and/or appropriately trained key study personnel will be present at the time of imaging. The anticipated time to complete all of the following is estimated to be about 60 to 90 minutes. Physiologic data, such as heart rate and respiratory rate, will be collected using a pulse-oximeter on the non-dominant hand and a chest plethysmograph around the subject's abdomen. These physiologic parameters have been shown to influence fMRI data acquisition and analysis. The following MRI scans will be acquired:

- **Baseline structural and resting state fMRI:**
Patients will be placed in scanner and acquisition of structural and resting state fMRI will be performed. Imaging will occur for a period of about 10-20 minutes while the patient is “resting” but not asleep.
- **fMRI in the presence of noxious stimulus:**

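### Central pain is assigned partly from systemic symptoms and Aim 2 then tests systemic symptoms across the same cohorts, so a significant result would not by itself support Hypothesis 2

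*Combined protocol and SAP*

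**What the plan says.** **Assignment.** Section 3.0, Phenotype Designation: "Patients will complete the Central Sensitivity Inventory questionnaire, the Fibromyalgia Diagnostic Tool, and the Head and Neck Pain Inventory to determine inclusion" in each cohort. It continues: "Using criteria established in the non-oncologic patient population, patients will be assigned to one of three cohorts by three independent reviewers", with two of three having to agree. The same paragraph says the patient's "responses will be reviewed by the principle investigator". No cut-offs are reproduced and no rule says how the three instruments combine. Section 10.0 lists the same instruments joined by and/or.

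**Content of the assigning instruments (section 4.0).**
- CSI: "Part A asks patients to identify systemic symptoms as being present" at a given frequency, and "Only Part A is used for scoring".
- FDT: "It combines the widespread pain index and the symptom severity scale". The protocol adds: "We will adapt the use of this diagnostic tool for the H&N cancer patient population".
- HNPI: a pain diagram with intensity, type and treatment of pain.

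**Outcome.** Hypothesis 2 (section 2.0) predicts more systemic symptoms, such as fatigue, neurocognitive dysfunction and depression, in the central cohort. Section 10.0 tests this by ANOVA across the three cohorts on subscales of the Vanderbilt Head and Neck Symptom Survey plus General Symptom Survey (VHNSS+GSS), the Profile of Mood States (POMS) and the Neurotoxicity Rating Scale (NRS). It names no contrast, adjustment or sensitivity analysis.

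**The concern.** The domain that helps place a patient in the central cohort is also the domain tested as that cohort's outcome. The background describes the amplified pain state as including "other systemic symptoms of neurological impairment such as fatigue, cognitive dysfunction, and mood disturbances", which is close to the list in Hypothesis 2. The forms differ, but a built-in difference needs only correlated content, not shared items.

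Nothing in the plan separates the two. Every patient also completes the Aim 2 forms, and no text says that the people assigning cohorts do so without seeing them. Two-of-three agreement improves reliability; it does not remove shared content.

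At stake is the reading of a positive Aim 2. Section 2.0 presents it as a hypothesis, section 10.0 gives it a significance test and a power statement, and the background says the answers will be the foundation for later studies. A result that is partly definitional could be carried forward as a finding.

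**Working it through.** **The plan's own figure.** Section 10.0 gives 25 per group for 80% power at a difference of 0.35. SD and alpha are not stated, so it cannot be reproduced. Read as Cohen's f at alpha 0.05, 0.35 needs 28 per group, and 25 give 76%. The present point does not depend on this; only the 25 per group is used below.

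**Model (all parameters assumed).** Among pain patients, let S be the symptom content of the assigning instruments and P the pain spread, both standard normal with correlation rho. Assignment score A = 0.5·S + 0.5·P; central means A above its 50th (or 70th) percentile. Outcome G = r·S + √(1−r²)·e. Take 25 central and 25 nociceptive, with a two-sided 0.05 test.

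**Middle case: rho = 0, r = 0.5.**
1. Symptom share of assignment variance = 0.5²/(0.5²+0.5²) = 0.50, so corr(S,A) = √0.50 = 0.707.
2. Median split: standardised A differs between halves by 2 × 0.798 = 1.596. Built-in difference = 0.5 × 0.707 × 1.596 = 0.56 SD.
3. Cut at the 70th percentile: 0.3477/0.3 + 0.3477/0.7 = 1.656. Built-in difference = 0.5 × 0.707 × 1.656 = 0.59 SD.
4. Median split: each group mean is 0.282 from zero, so the within-group SD is √(1−0.282²) = 0.959 and the standardised difference is 0.564/0.959 = 0.588. Noncentrality = 0.588 × √(25/2) = 2.08, giving 53% rejection. Simulation gives 52-57% over both cuts.
5. The same 50 patients regrouped on P alone: about 5%.

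**How far the assumptions move it** (rho = 0, median split, built-in difference = 1.596 × √share × r; last column from 2,000 simulated trials per row):

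| Symptom share of assignment variance | r | Built-in difference (SD) | Contrast significant in predicted direction |
|---|---|---|---|
| 0 | 0.5 | 0 | 3% |
| 0.25 | 0.3 | 0.24 | 13% |
| 0.25 | 0.5 | 0.40 | 29% |
| 0.50 | 0.5 | 0.56 | 52% |
| 0.75 | 0.7 | 0.97 | 97% |

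**If pain and symptoms are correlated** (share parameters and r as in the middle case):

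| rho | Full phenotype rejects | Pain-only rejects |
|---|---|---|
| 0 | 53-57% | 5% |
| 0.3 | 66-69% | 13-14% |
| 0.5 | 72-75% | 30% |

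At rho = 0.5, corr(S,A) = √(1.5/2) = 0.866. The full-phenotype difference is 0.5 × 0.866 × 1.596 = 0.69 SD and the pain-only difference is 0.5 × 0.5 × 1.596 = 0.40 SD.

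**Why the three-group ANOVA is the wrong yardstick.** In the middle case, with the no-pain mean set at the pain patients' average, it rejects in 42-48% of trials. With no symptom selection at all but a no-pain mean 0.5 SD lower, f = 0.5 × √2/3 = 0.236, noncentrality = 0.236² × 75 = 4.17, and it rejects in 42%. One rejection rate, two unrelated causes.

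**The case against.** **Central pain includes systemic symptoms, so this is the construct and not a flaw.** This stands as a reason not to redefine the cohorts or to replace the planned comparison. A pain-only rule tests pain distribution and not the syndrome the background describes. But if symptoms are part of the definition, their excess in that cohort is to that extent not separate evidence for Hypothesis 2.

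**The assignment rule may give symptoms little weight.** This stands. The protocol points to outside criteria that cannot be seen here, and the and/or wording in section 10.0 would literally permit assignment from the HNPI alone, in which case nothing is built in. A reader might infer that bias toward Hypothesis 2 is certain, or that Aim 2 must come out positive. The documents do not support either: a built-in difference requires that symptoms carry weight and correlate with the outcomes.

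**Correlation between pain spread and symptoms may be real.** It may. It could reflect shared self-report or be essentially what Hypothesis 2 claims, and these data cannot separate the two. The 30% pain-only rejection at rho = 0.5 could be power for a true difference.

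**Other parts of the study help.** Section 2.0 also plans to relate MRI signatures to systemic symptoms. That is partial help: section 10.0 specifies no such analysis, and the signatures are to be derived from these same cohorts.

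**Regrouping afterwards is not clean.** Correct. The patients were still recruited on the full phenotype. In extreme illustrations where the middle 40% go unassigned, pain-only grouping still rejected in 15-21% of trials at rho = 0.

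**Conclusion.** The point holds in a conditional form. Systemic-symptom content enters cohort assignment, the same domain is the Aim 2 outcome, and the plan neither acknowledges nor examines the overlap. A significant Aim 2 result would therefore not by itself support Hypothesis 2. The omnibus test adds a second reason: it is non-directional and can be significant from no pain against any pain.

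The size cannot be stated from the documents. It runs from nil, if symptoms have no weight, to large. The 52-57% against 5% is an illustration that rests on a half share of assignment variance, a correlation of 0.5 with the outcome and no pain-symptom link.

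A reader might take the ANOVA rejection rates as the measure of circularity, or conclude that the assignment forms and the outcome forms are the same. Neither is supported: the first depends on an unstated no-pain mean, and the second is contradicted by the instrument lists. The data remain usable, so this is something to fix in the analysis plan and not a reason to change recruitment.

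**What to change.** Keep the full phenotype for Aim 1, for filling the MRI cohorts and for the planned Aim 2 comparison. In section 10.0:

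1. State as a limitation that the CSI and FDT share symptom content with the Aim 2 outcomes.
2. Make the direct central-versus-nociceptive contrast the comparison that bears on Hypothesis 2.
3. Treat the VHNSS pain domain as descriptive, since the cohorts are defined by pain.
4. Pre-specify a sensitivity analysis that regroups pain patients from the stored FDT widespread pain index and HNPI only, by a rule written before any Aim 2 outcome is analysed. Give this grouping its own label.
5. Where available, report the slowly repeated evoked pain result by group as a supporting check. It is not a listed assignment input. For the three subjects tested before it was added, section 3.0 promises only an attempt at repeat testing, so it may be missing.
6. Call Hypothesis 2 supported beyond definition only if the contrast persists in the sensitivity analysis, and write down in advance what persists means.

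**Cost.** A written rule and a little more analysis; no new data, because section 9.0 has all forms entered in REDCap.

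**Downsides.**
- The pain-only grouping addresses pain distribution and not the full syndrome.
- Groups may be unequal. For an assumed 0.8 SD contrast, power is 79% at 25/25, 72% at 15/35 and 60% at 10/40.
- The difference may be diluted (0.69 to 0.40 SD at rho = 0.5, where the contrast rejects in only about 30% of trials), so a non-significant result does not refute Hypothesis 2. Report the estimate with its interval.
- It does not remove correlation from shared self-report, or all of the selection from recruiting on the full phenotype.
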